This method of recruitment and sampling limits the amount of information to be collected each month, enables the tracking of patients each month to maintain the open cohort within each clinic, it simplifies the sampling process, and maintains patient confidentiality.

[figure not shown]
The research participation response rate experienced by our partners range from 60-80% and we will sample 30 patients each month to achieve our target sample of 20 per month.

Methods: Assignment of interventions

A number of outcomes will be collected by interviewing a random sample of 20 patients who have received a consultation in the previous month. To reduce the transfer of patient identifiable data and their contact details, we specify the following sampling protocol. On the first calendar day of each month the list of patients who have had at least one consultation in the preceding month will be aggregated within each cluster site by the facility representative. The list will be pseudonymised by redacting identifiable information including patient name and contact details but keeping unique IDs, such as row numbers, and other basic data to permit comparisons between sampled and interviewed

groups for quality control. The list will be photographed and sent to the trial statistician, who will send back a random sample. Data collection from the selected patients can then proceed.

Figure 1: Cluster randomisation sequencing

Allocation

Within each country the 20 participating clusters will be randomised to one of ten sequences (see figure 1) with two per sequence. A random number will be generated for each cluster and then clusters assigned to each sequence in ascending order of the generated number. The randomisation will be conducted by the trial statistician who will be blinded to cluster name. The intervention implementers and clinics will not be blinded to allocation sequence as this is impractical given the need to plan and prepare training.

Blinding

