Appendix 1 shows the data flow for patient participants through the trial.

Statistical methods

The data from each trial will be analysed using a generalised linear mixed model framework standard for stepped-wedge cluster designs[16]. Data from each time point are considered a repeated cross-section given the difficulty linking observations between patients in different time periods. The primary outcomes are of two types: count data (the number of consultations by mode of delivery and the number of prescriptions) and a continuous score (the patient trust outcome). For the former we

specify the following log-linear model, for patient $i = 1, \dots, N$ in cluster $j = 1, \dots, J$ at time period $t = 1, \dots, T$ with number of events y_{ijt}^1 :

$$y_{ijt}^{(1)} \sim \text{Poisson}(\lambda_{ijt})$$

$$\lambda_{ijt} = N_{jt} \exp(\eta_{ijt}^{(1)})$$

where N_{jt} is the denominator population (i.e. the number of active patients in cluster j at time t) and η_{ijt} is the linear predictor. For the continuous outcome y_{ijt}^2 we specify:

$$y_{ijt}^{(2)} \sim N(\eta_{ijt}^{(2)}, \sigma^2)$$

The specification of the linear predictor in both models takes the form:

$$\eta_{ijt} = x'_{ijt}\beta + z'_{jt}\gamma + \delta D_{jt} + \alpha_j + \psi_{jt}$$

where x_{ijt} is a vector patient-level covariates, z_{jt} is a vector of cluster-level covariates, D_{jt} is an indicator equal to one if cluster j has the intervention at time t and zero otherwise, and $\alpha_j \sim N(0, \sigma_\alpha^2)$ and $\psi_{jt} \sim N(0, \sigma_\psi^2)$ are cluster, cluster-time and individual random effects respectively. The treatment effect of interest from the Poisson model is an incidence rate ratio, although we will also provide absolute treatment effects for context, and from the linear model we will report only absolute treatment effects.

Inference

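### The written stepped-wedge model has no calendar-month effect, so about half of any linear secular trend would be counted as an effect of training

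*Protocol*

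**What the plan says.** The Statistical methods section of the protocol adopts a "generalised linear mixed model framework standard for stepped-wedge cluster designs". It then gives one equation for the Poisson and Gaussian models, introduced by "The specification of the linear predictor in both models takes the form". The terms are:

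- a patient-level covariate vector x with coefficients β;
- a vector z with coefficients γ, of which the text says only that it "is a vector of cluster-level covariates";
- δ times the indicator that cluster j has the intervention at time t;
- a cluster effect α and a cluster-time effect ψ, both normal with mean zero.

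No term for calendar month, fixed or otherwise shared by all clusters, is written there or described elsewhere in the protocol. The sentence after the equation says that the random terms "are cluster, cluster-time and individual random effects respectively", which is three names for two symbols.

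The Inference section says that point estimates, confidence intervals and p-values will be reported without claims of statistical significance. The p-values come from re-randomising clusters to sequences. The Sample size section says that the minimum detectable effects (MDEs) rest on the models given later in the protocol.

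**The concern.** Every cluster moves from untrained to trained as the months pass, so the training indicator and calendar time are strongly correlated by construction. If attendance, phone use or trust changes over the year for reasons that affect all clusters, a model without month effects has only δ and the random effects with which to explain the change. The term ψ does not help: it has mean zero and is specific to each cluster and month, so it does not model a shift common to all clusters.

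The protocol does not say how large such shifts will be. It does expect further peaks of communicable disease such as COVID-19 during the project (Research deliverables), so they are plausible. All four primary outcomes use this predictor. Because the protocol declines to rest its conclusions on significance, the estimates and intervals carry the inference, and these are the quantities that a trend would distort.

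**Working it through.** **Inputs.** All are from the protocol unless marked as assumed.

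- 20 clusters per country, ten sequences, two clusters per sequence (Allocation).
- 12 monthly periods from the participant timeline (months 2 to 13), or 13 from Table 1. Both were run. The sequence figure is not available, so the month of the first step is assumed. It makes no difference at T = 12 and almost none at T = 13.
- Trust: SD 0.5, 20 completed surveys per cluster-month (Sample size table).
- Power 80%, type I error 5%, ICC 0.05, CAC 0.8 (Sample size); two-sided tests (Inference).

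**Variance components for trust.** Total variance is 0.5² = 0.25.

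- Cluster: 0.25 × 0.05 × 0.8 = 0.0100.
- Cluster-time: 0.25 × 0.05 × 0.2 = 0.0025.
- Sampling variance of a cluster-month mean: 0.25 × 0.95 / 20 = 0.011875.

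The covariance matrix of one cluster's monthly means is V = 0.0100·J + 0.014375·I, where J is the matrix of ones. The variance of the estimate of δ is the corresponding diagonal element of (Σ X′V⁻¹X)⁻¹, summed over clusters. X holds the training indicator plus either an intercept (as written) or one indicator per month. MDE = (1.960 + 0.842) × SE = 2.802 × SE.

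**Step 1: reproduce the stated trust MDE of 0.07.**

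| Model | T = 12 | T = 13 |
|---|---|---|
| With month effects | SE 0.0263, MDE 0.074 | SE 0.0258, MDE 0.072 |
| As written | SE 0.0174, MDE 0.049 | SE 0.0164 to 0.0166, MDE 0.046 to 0.047 |

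Only the model with month effects rounds to 0.07. The face-to-face and prescription pair (0.84 / 1.20) points the same way. Under one conversion of the ICC to the log scale, it comes out at 0.83–0.84 / 1.19–1.20 with month effects and 0.89–0.90 / 1.12–1.13 without. That conversion is an assumption. Two others give about 0.86–0.87 / 1.14–1.16 with month effects.

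**Step 2: bias from a common trend.** The true effect is set to zero and every cluster's mean rises by one unit a month. The expected estimate of δ is then the bias per unit of monthly drift.

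| Model | T = 12 | T = 13 |
|---|---|---|
| With month effects | 0 | 0 |
| As written | 5.81 | 6.34 |
| As written, share of the total change | 5.81 / 11 = 0.53 | 6.34 / 12 = 0.53 |

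**Step 3: illustrative sizes.** The drifts are assumptions.

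- Trust drifting by 0.012 a month: 0.012 × 5.81 = 0.070 (T = 12) or 0.012 × 6.34 = 0.076 (T = 13).
- Trust drifting by 0.10 over the whole trial: 0.10 × 0.528 = 0.053, against a model-based SE of 0.0174 at T = 12. A Wald test would reject about 86% of the time.
- Face-to-face visits rising by 20% over the trial: exp(0.53 × ln 1.2) = a spurious rate ratio of about 1.10.

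**Step 4: permutation.** In 200 simulated trials with a total drift of 0.20, no true effect and 499 re-randomisations each, the model as written gave a mean estimate of 0.105. The permutation test rejected in 5% and the Wald test in 100%. The permutation distribution moves with the trend, so the p-value keeps its level while the estimate does not.

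**The case against.** The strongest reply is that the equation is shorthand. It shows no intercept either, and nobody would fit the model without one. The vector z carries a time subscript and could hold month indicators, the framework is described as standard for the design, and the trust MDE matches only when month effects are present. This is a good argument that month effects were intended, and that part stands. It does not remove the point: z is defined as cluster-level covariates, and an analyst who followed the equation as defined would obtain a biased estimate.

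Four stronger readings may tempt a reader, and the documents do not support them.

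- **That any time trend is read in full as a training effect.** Only about half of a linear trend is, and no bias arises if there is no trend.
- **That the MDE table proves a different model was used.** The evidence is partial. The remote-consultation pair was not reproduced, and the protocol itself gives two versions for the same design (0.77 / 1.56 in Sample size, 0.73 / 1.38 in Appendix 5). The revised Tanzania trust value of 0.08 fits neither model: 0.088 to 0.095 with month effects and 0.050 to 0.064 without, over 7 to 10 assumed periods.
- **That the reason given for the cross-sectional analysis is wrong and should be deleted.** The protocol says "Data from each time point are considered a repeated cross-section given the difficulty linking observations between patients in different time periods", yet it also says that its recruitment method "enables the tracking of patients each month to maintain the open cohort within each clinic". That tracking concerns facility records. For the surveys, the monthly sampling list may carry only row numbers, linkage to facility data depends on consent, and no repeat survey of the same person is planned.
- **That a patient random intercept must be added to gain precision.** If each person is surveyed once, a patient effect in the Gaussian model cannot be separated from residual error, and the gain is nil. Any other figure depends on within-patient correlations that the protocol does not give.

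**Conclusion.** The point holds as an omission in the stated model. As written, both predictors lack a calendar-month effect, and about 53% of a linear change common to all clusters would pass into δ. For trust this is 5.8 to 6.3 times the monthly drift in the ten-sequence design. These multipliers follow from the design and from the protocol's ICC and CAC, given 12 or 13 monthly periods. The drift sizes are assumptions, so the bias is conditional on a trend and is not shown to occur. The permutation p-values are not affected in level; the reported estimates and model-based intervals are.

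The agreement of the trust MDE with a model that includes month effects suggests that the term was meant to be there. The mismatch between three named random effects and two in the equation is a separate, minor slip and does not cause the trend bias.

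**What to change.** Write a fixed effect for each calendar month into the linear predictor of both models, and state that this same model is fitted within the permutation procedure. In place of a single intercept this takes 11 extra parameters at 12 periods, or 12 at 13 periods. It leaves the stated trust MDE of 0.07 unchanged, because that figure is already reproduced only with month effects. The cost is a change of wording in the protocol and in any SAP that repeats the equation.

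For the random effects, either give the individual effect a symbol, a variance and a place in the equation (for example, for the facility-record counts, where patient IDs are tracked monthly), or delete the word.

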REmote Consulting in Healthcare (REaCH) training has a remote knowledge cascade process and has been piloted, evaluated and upscaled within parts of rural Tanzania. REaCH training is delivered in English and cascaded in local languages [7]. REaCH is scalable across LMIC countries with limited/variable digital infrastructures. Trained primary care health workers can replace 10 face-to-face consultations with remote consultations daily. Cascading to 50 others results in 510 remote consultations daily. During the project, existing in-country stakeholder groups will work to influence health policy at government levels regarding airtime and professional regulation [3,5].

Novel evidence for health workers' ability to deliver trustworthy and safe remote healthcare that patients report as non-inferior to face-to-face care, will both protect communities and their health workers during times of need. It will sustainably strengthen health systems in LMIC. We progress the UN sustainable goals 3.1-3.5, 3C and 3D in achieving good health and well-being [8].

A scoping review of Medline, Google Scholar and recent special issues of Journal of Medical Internet Research for 2020 research on remote consulting identified literature from high income countries and China which included commentaries on its role (e.g. for cancer care, diabetes), reports of how it has been implemented, what it has been used for and by whom (e.g. in Western China, US) and,

surveys of healthcare providers on how they are delivering remote consulting and of patients on their preferences. There was no evidence on whether rapid change to remote consulting in these countries resulted in healthcare that was trustworthy and safe.

Our own 2020 published review and framework focused on delivery of remote consulting to marginalised communities of low-middle-income countries [3]. We found published evidence of effectiveness of specific projects providing remote consulting for specific health conditions alongside traditional face-to-face care and evidence that some health workers used their own phones informally. There were no studies that reported on trustworthiness and safety in replacing face-to-face with remote consulting.

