The 2019 World Health Organization recommendations on digital interventions for health system strengthening, have little to say about remote consulting for poor marginalised communities, being largely based on evidence from well-resourced settings. Our 2020 published review [3] draws on socio/economic/behavioural/medical evidence to identify the potential benefits and hazards of remote consulting including change in patient/provider trust and thresholds for diagnostic/treatment action depending on how it is delivered. There is a gap in the evidence relating to how remote consulting can be delivered in LMIC. There is no international evidence on its impact on indicators of quality in healthcare delivery.

Research hypothesis

REaCH training will increase the rate of remote consulting. This remote consulting will not affect patient trust in, and the safety of, primary care consultations for long-term conditions.

Objectives

We aim to deliver internationally unique evidence on a remote consulting training scheme, whether it is effective in increasing remote consulting, whether it affects face to face consulting, and whether it changes patient reports of trustworthiness and changes specified indicators of safety of healthcare consultations in primary health care in Tanzania and Nigeria. Alongside runs south-south collaboration with Uganda and Kenya. We propose two trials to deliver evidence for different African contexts. A process evaluation will inform implementation across East and West Africa.

Trial research questions

To what extent does REaCH training affect:

1. Patient consultation rates delivered face-to-face and remote?
2. Patient perceptions of the trustworthiness of health workers providing consultations?
3. The medication prescription issue rate?
4. Missed appointment rate?
5. Medical investigation issue rate?
6. Patient health activation levels?

Process evaluation research questions

1. What is the impact of REaCH training on patient and health worker experience with healthcare?
2. What enables and hinders health workers in deploying remote consulting?

Trial design

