We propose four primary outcomes, detailed below, to test our research hypothesis. Multiple primary outcomes are recommended against by some guidance for cluster trials (e.g. CONSORT) [10] as it "incurs the problems of interpretation associated with multiplicity of analyses". However, we opt for multiple primary outcomes here as the intervention is multi-faceted and may affect different aspects of patient care and their interaction with the health system in different ways. Appropriate inferences about the functioning of REaCH cannot be made on the basis of any singular outcome. We ensure appropriate correction for multiple testing for all our test statistics (see Statistical methods). Furthermore, we will not be using 'statistical significance' to make inferences about the effectiveness or not of the intervention, given the importance of including the full range of qualitative and quantitative evidence to make conclusions about the effectiveness of REaCH, which also limits the risk of faulty inferences made through the use of multiple primary outcomes. Our unit of analysis for all outcomes is at the individual level.

Primary outcomes:

- 1) Trust in healthcare provider: Physician Humanistic Behaviour Questionnaire (PHBQ) [11] determines the degree to which healthcare providers communicate humanistically with their patients. Humanistic communications engender trust between the patient and the healthcare worker. The PHBQ has face and content validity with patients and health workers for assessing these behaviours during remote consultations [12].
- 2) Face to face consultation rate: the number of visits per month for the eligible patient population where the patient is seen in person by the consulting health worker.
- 3) Remote consultation rate: the number of visits per month for the eligible patient population conducted using a telephone.
- 4) Prescribing rate: the number of prescriptions issued and collected to the eligible patient population per month. This outcome is a proxy for patient safety as a change in this outcome is an indicator of changes in safety and confidence. The meaning and impacts of changes in this indicator will be explored in the process evaluation.

Secondary outcomes:

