- 5) Patient engagement with their health: Patient Activation Measure (PAM-13) aims to understand the knowledge, beliefs and skills required by people to enable them to manage their long-term conditions [13]. It has been successfully used in African populations [14]. Our previous research found that patient activation increases with remote consulting [4]. Also that the PAM-13 [12] has face and content validity for assessing the impact of remote consulting.
- 6) Patient safety is assessed by counting the number of investigations processed by the facility monthly and matching these to the patient’s consultation type. An increase may indicate a higher safety threshold when the person cannot be examined. A decrease may indicate missed health needs. The meaning and impacts of changes in this indicator will be explored in the process evaluation.

Evidence from the secondary outcomes will be explored in the process evaluation.

Sample size

The trials in Nigeria and Tanzania will take place independently, but with identical designs. We plan to recruit 20 clusters in each country for the trial and we expect there to be an average of 100 active eligible patients at any one time in each cluster. We describe each of these active patients in each cluster as an open cohort- patients will leave the cohort if they are not seen for >5 months and newly diagnosed patients meeting the eligibility criteria can join the cohort. The trial has both non-inferiority and superiority inferential goals: we hypothesise the intervention will increase the remote consultation but not affect consultation trust, for example. We therefore opt to determine “minimum detectable effect” sizes rather than power to indicate the precision of the trial and the likely sizes of effect for which we can provide strong evidence of superiority or non-inferiority. Our calculations are based on the statistical models reported below and a power of 80%, a type I error rate of 5%, an ICC of 0.05, and a CAC of 0.8. The assumptions about each outcome and minimum detectable effect sizes are reported in the Table below.

| Outcome | Baseline assumed | Denominator or population | Treatment effect | Lower minimum | Upper minimum |
|----------------|-------------------------|----------------------------------|-------------------------|----------------------|----------------------|

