|----------------|-------------------------|----------------------------------|-------------------------|----------------------|----------------------|

| | | | | detectable effect | detectable effect |
|--|--|-----------------------------|----------------------|--------------------------|--------------------------|
| Face to face consultation/prescription rate | 0.25 consults/prescriptions per person-month | All active patients (n=100) | Incidence rate ratio | 0.84 | 1.20 |
| Remote consultation rate | 0.02 consults per person-month | All active patients (n=100) | Incidence rate ratio | 0.77 | 1.56 |
| Patient trust | 3.5 (sd=0.5) | Sampled patients (n=20) | Absolute effect | -0.07 | 0.07 |

A change in either consultation rate of an equivalent of one visit per person-year is considered “clinically significant”, which is well outside our minimum detectable range. Similarly, we will be able to identify reasonably small changes (~0.15 standard deviations) in patient trustworthiness score, although we do not hypothesise a change in this outcome.

Patient participant recruitment and sampling

At the study commencement each cluster provides the study with a pseudonymised list of active patients, giving us a patient ID and the basic information, we need from each patient (age, sex and eligible diagnosis). At the clinic they will have a link to patient ID with the patient’s record but we will not have access to the patient personal data. This is the open cohort for each cluster.

Each month we collect from each clinic a record of the consultations conducted and prescriptions and investigations ordered by the clinic, all they need to provide is the number of visits by type, prescriptions, investigations and any other information we need linked to a patient ID (e.g. patient 1234 had one remote visit, 2 prescriptions). Any additional patients can join the open cohort if they become eligible during the trial period.

Using the information, the research team can calculate outcomes, remove patients that are no longer active/who default, and sample for participation in the trust and patient activation outcomes and the process evaluation interviews. We will return the list of sampled patient identification number to the clinic for them to contact the potential participant so the research team can commence the informed consent processes.

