All models will be estimated using restricted maximum likelihood using the R package lme4. We will report point estimates, confidence intervals, and p-values but not make any claims of “statistical significance” given recent strong arguments against doing so[17]. P-values will be based on the null hypotheses $H_0: \delta = 0$ versus the two-sided alternatives $H_1: \delta \neq 0$ in each of the models. Given there are multiple primary outcomes we will adjust reported p-values for multiple testing using a stepdown method, which provides an efficient means of controlling the family-wise error rate[18]. We will derive the exact distributions of the test statistics to perform the stepdown procedure using a permutation test approach, by re-randomising clusters to different sequences in the stepped-wedge design[19]. This method ensures appropriate control of the family-wise error rate and avoids potential biases resulting from small numbers of clusters.

Data management

Each country team will store consent forms and raw data on their own university secure password protected server or if paper-based, such as consent forms, in a locked filing cabinet. The data will be electronic in an email attachment, or a photo of a list, or entered into a survey software, on the REaCH Moodle or a digital recording. The exact nature of the raw data will depend on the available infrastructures of individual clusters and their geographical proximity to the university. Data will be translated as necessary and transcribed locally. We will ensure a confidentiality agreement is in place for all transcribers. Two members of the local country team (one unblinded) will have access to a list which links a patient identifier to their identity and their informed consent forms. For REaCH trainees this will be three people because the facilitators will also know their identity and have access to their Moodle data. These will remain stored locally throughout the trial and not leave the country.

In Tanzania, data will be stored virtually in a server at Commission for Science and Technology (COSTECH) [name]. Email: [contact] Research Registry Office [contact]

Physical data will be stored at St. Francis University College of Health and Allied Sciences, Ifakara Health Institute (IHI), [name].

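### Non-inferiority is a stated goal for trust and safety, but every primary outcome is tested only against zero effect, and trust and prescribing have no margin

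*Protocol*

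**What the plan says.** **The goal.** The Research hypothesis section of the protocol states: "This remote consulting will not affect patient trust in, and the safety of, primary care consultations for long-term conditions". The background speaks of care "that patients report as non-inferior to face-to-face care". Sample size says: "The trial has both non-inferiority and superiority inferential goals". Below the table of detectable effects, the text adds for trust "although we do not hypothesise a change in this outcome". Prescribing is the primary outcome that stands for safety; under Outcomes the protocol explains: "This outcome is a proxy for patient safety as a change in this outcome is an indicator of changes in safety and confidence".

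**The test.** Under Inference, "P-values will be based on the null hypotheses" that the treatment effect is zero, against two-sided alternatives, in each of the models. The same paragraph continues: "Given there are multiple primary outcomes we will adjust reported p-values for multiple testing using a stepdown method", with the null distribution obtained by re-randomising clusters to sequences.

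**What could serve as a threshold.**
- Sample size calls a change of one visit per person-year clinically significant, but says so for the two consultation rates only.
- For trust it gives a minimum detectable effect (MDE) of 0.07 points either way, about 0.15 standard deviations, as an indication of precision.
- The 40% difference under Harms is a monitoring trigger.
- No margin appears for trust or prescribing.

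The protocol also says that point estimates and confidence intervals will be reported, that no claims of statistical significance will be made, and that conclusions will draw on qualitative and quantitative evidence together.

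**The concern.** A test of zero effect can give evidence that something changed. It cannot give evidence that nothing important changed, because a large p-value arises both when the effect is negligible and when the data are too imprecise to show it. For trust and prescribing the costly error is to overlook a real deterioration. The specified test guards against the opposite error, falsely declaring a change, and the upward adjustment of the p-values strengthens that guard at the expense of detection.

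The confidence intervals could carry the claim, but only against a limit set beforehand. Without one, the difference that counts as unimportant can be chosen after the interval has been seen. At stake is the part of the hypothesis concerning trust and safety, which covers two of the four primary outcomes.

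**Working it through.** **1. Reproduce the protocol's trust figure.**

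Inputs from the protocol: SD 0.5, 20 sampled patients per cluster-month, ICC 0.05, CAC 0.8, 20 clusters in ten sequences of two, power 80%, two-sided 5%. The sequence figure is not shown, so the number of monthly periods is an assumption. Twelve is used (data are supplied in months 2 to 13), with 11 and 13 as alternatives.

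Model: linear, with fixed period effects and random cluster and cluster-period effects. The variance components are:
- total variance 0.5² = 0.25
- cluster 0.25 × 0.05 × 0.8 = 0.0100
- cluster-period 0.25 × 0.05 × 0.2 = 0.0025
- residual variance of a cluster-period mean 0.25 × 0.95 / 20 = 0.0119

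Generalised least squares gives the SE of the treatment effect, and MDE = (1.960 + 0.842) × SE = 2.802 × SE.

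| Periods | SE | MDE | MDE in SD |
|---|---|---|---|
| 11 | 0.0270 | 0.0756 | 0.151 |
| 12 | 0.0263 | 0.0738 | 0.148 |
| 13 | 0.0258 | 0.0723 | 0.145 |

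Twelve periods reproduce the printed 0.07 and the stated 0.15 SD.

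**2. What the zero-effect test does when trust really falls by the MDE.**

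By definition the loss is then 2.802 standard errors. The chance of a non-significant result is 1 − Φ(2.802 − critical value).
- Unadjusted 5%: 1 − Φ(2.802 − 1.960) = 1 − 0.80 = 20%.
- Bonferroni-type first step, 0.05/4 = 0.0125: 1 − Φ(2.802 − 2.498) = 1 − 0.619 = 38%.
- Second step after one rejection, 0.05/3: 1 − Φ(2.802 − 2.394) = 34%.

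The last two are upper approximations. A permutation stepdown uses the joint distribution of the statistics and is less severe when outcomes are correlated.

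**3. How precision enters.**

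Take a true loss of exactly 0.07 and the unrounded SE of 0.0263. This ratio is 2.658 instead of 2.802, so the first row is slightly above the figures in step 2.

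| SE | Non-significant at 5% | Non-significant at 1.25% | Non-inferiority wrongly shown, assumed margin 0.07 |
|---|---|---|---|
| as planned | 24% | 44% | 2.5% |
| × 1.5 | 57% | 77% | 2.5% |
| × 2 | 74% | 88% | 2.5% |

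Non-significance becomes more likely as precision falls. The error of the margin-based rule does not change.

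**4. Why the MDE is not a margin.**

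Appendix 5 gives a trust MDE of 0.08 for the shortened Tanzania trial, against 0.07 originally. What counts as an important loss of trust cannot have changed because the trial became shorter. Taking both printed figures at face value, the redesign SE is 0.08 / 2.802 = 0.0286. The chance that the unadjusted test misses a true 0.07 loss is then 1 − Φ(0.07/0.0286 − 1.960) = 31%, up from 20%.

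**5. Is a margin-based analysis feasible at the planned size?**

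The protocol gives no trust margin, so a range is assumed: SE 0.0263, true difference zero, one-sided 2.5%, power = Φ(margin/SE − 1.960).

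| Assumed margin | Power |
|---|---|
| 0.05 | 48% |
| 0.07 | 76% |
| 0.10 | 97% |
| 0.15 | >99% |

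For prescribing, the same method with Poisson variance and 12 periods gives an SE of 0.0644 for the log rate ratio. The detectable ratios are then 0.835 and 1.198, against the printed 0.84 and 1.20. Suppose, purely for illustration, that the consultation threshold were borrowed: (0.25 ± 1/12)/0.25 = 0.67 and 1.33. The upper side governs: Φ(ln 1.33/0.0644 − 1.960) = Φ(4.47 − 1.96), about 99%.

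**The case against.** The strongest reply is that the protocol does not rest inference on significance at all. It disclaims such claims, reports intervals and brings in the process evaluation. A reader might infer from the plan that a large p-value will be counted as support for no effect, so that an imprecise trial would be rewarded. The documents do not say this. It would follow from one way of reading the results, and the miss rates in steps 2 to 4 apply only under that reading. An imprecise trial would also display a wide interval.

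It would likewise go too far to say that the trial can draw no conclusion about trust. The objectives and research questions ask to what extent the training changes each outcome, and two-sided estimation suits that. The non-inferiority phrase in the background describes intended impact. A reader of the intervals could still judge whether a large harm is excluded.

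A reader might further infer that the intervals will lack the small-cluster and multiplicity corrections. The protocol describes these for test statistics and p-values and does not say how the intervals are built. That is commonly settled in an analysis plan, and silence is not evidence of an error.

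Finally, a clinical threshold does exist for the two consultation rates, so the gap is confined to trust and prescribing.

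All of this narrows the point without removing it. The protocol names non-inferiority as a goal and fixes a null hypothesis that does not address it. Disclaiming significance does not supply the limit against which an interval must be read.

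**Conclusion.** The point holds in this limited form: the stated null does not fit the stated goal for trust and prescribing, and neither outcome has a margin. The planned p-values cannot establish the no-effect part of the hypothesis, and the intervals lack a pre-stated criterion. This is a mismatch within the protocol and does not depend on what an analysis plan might add.

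The size is conditional. The 20% rests on the protocol's own power and type I error. The 38% is an upper approximation, and the 31% for Tanzania relies on the printed MDEs. The power figures after the fix assume 12 periods, no true difference and margins that are not the protocol's. They show feasibility and do not recommend a value.

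**What to change.** - **Remote consultation rate:** keep the two-sided test of zero effect.
- **Trust:** before analysis, state a non-inferiority margin justified on substantive grounds and not taken from the MDE.
- **Prescribing:** state a two-sided equivalence range, since the protocol treats a change as a safety signal without giving a direction. The investigators must decide whether the consultation threshold has any bearing here.
- **Face-to-face rate:** state an equivalence range only if the rate is to be described as unaffected.
- **Decision rule:** conclude non-inferiority or equivalence only if the confidence interval excludes the margin; otherwise report the result as inconclusive.
- **Multiplicity:** say how these outcomes enter the family. If trust and safety must both hold for the claim, no adjustment between them is needed.
- **Intervals:** preferably obtain them by inverting the permutation test already planned.

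The cost is protocol or analysis-plan wording and some computing, with no added patients. The drawback is that the trust or safety claim may end as inconclusive, most likely if the justified trust margin is near 0.05 points or if precision falls short of plan.
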